Explain how parents/guardians will be presented with the information needed to decide to allow their children to participate, including all elements of informed consent.

FGID module, retrospective/prospective reviews: N/A - We will not obtain parental consent for the inclusion of their children's data in the data reviews. We are seeking a waiver of parental consent for this portion of the research. A002 Tool usability questionnaire: The potential participant will have no interaction with a research team member at the point the questionnaire opportunity is introduced. We will inform prospective subjects about the research opportunity via a SIS. It is not practical to obtain signed consent. If the individual agrees to participate by voluntarily proceeding to questionnaire, consent is implied. A003 Tool usability questionnaire: The 14-17 year old will assent for self, parental consent deemed not feasible and waiver parental consent requested for this age group. For patients 14-17 year old, the parent has limited permissions to access the patient's MyChart account. This age group will complete the FGID module independently or with assist if they choose. We request a waiver of parental consent since the 14-17 year old has their own account and thus getting parental consent is not feasible. Survey(online and phone): Phone: For the phone surveys, we will seek verbal consent from the parent for the child's participation. The RA will verbally review the SIS/Auth form

over the phone and answer any questions before obtaining verbal consent and auth from the parent the participation of the minor/patient if age 10-17 years old. Online: A MyChart message will be sent to the patient/patient proxy to introduce the study opportunity. This introduction will include the SIS/Auth and a time limited participant specific link to the REDCap e-consent. (Patient communication uploaded in Notes and Attachments). Recognizing that the MyChart account for patients 14-17 may not have a parent proxy assigned, a statement is added to the introduction requesting interested teens share this study information with a parent/legal guardian for consideration and consent.

q23780

Describe any informed consent tools which will be used to present information (i.e. consent documents, videos, brochure, drug/device information, etc) and how they will be used.

FGID module, retrospective/prospective reviews: N/A Survey(online and phone):  
SIS/Auth form A002 Tool usability questionnaire: Study Information Sheet

q23784

Describe the timing of the informed consent process, including how you will ensure parents/guardians have sufficient opportunity to discuss and consider their children's participation before agreeing to allow their children to participate in the research.

FGID module, retrospective/prospective reviews: N/A Survey(online and phone):  
Phone: The informed consent process for phone surveys will take place over the phone when the patient and parent indicate their interest and availability. Any participants wishing more time to consider will be called back at a different time.  
Online: After reviewing the MyChart recruitment message, the potential participant will be able to advance directly to the online enrollment process when they desire.  
A002 Tool usability questionnaire: After the parent, parent/patient dyad, or patient (add A003 "or patient") has completed the FGID module, expressed interest in providing feedback, read the SIS, and implied consent by voluntarily proceeding to the questionnaire.

q30127c

Will you include all required elements of consent in your consent process?

Yes

q23789

Indicate in what language(s) the consent conversation will be conducted.

English

q23793

Explain how you will ensure parents/guardians understand the information you have presented to them before they agree to allow their children to participate in the research.

FGID module, retrospective/prospective reviews: N/A Survey(online and phone): Phone: An RA will ask participants if they have any questions (and provide the answers to those questions) before the subject agrees to participate. Online: The e-consent instrument will contain instructions for completion. Within those instructions will be PResNet contact information for questions. If participants proceed without asking questions, it is implied that the content was understood. A002 Tool usability questionnaire: Participants will voluntarily agree to fill out questionnaire before being presented with the survey. If they do not understand the content or choose not to participate, they are given the option to decline participation.

q23798

Briefly describe any training provided to investigators who are obtaining informed consent.

Phone surveys: Research Assistants have been trained in obtaining informed consent (and assent) through online CITI training, university-sponsored training, and internal training and QA programs.

q23800

Does the research include any minimal risk procedures to which parents/guardians will not consent for their children to participate?

No

q30330

For those parents/guardians who will consent to allow their children to participate, choose whether the consent process will be documented by a written signature.

Some parents/guardians will provide a written signature as documentation of consent, and some will not.

q30331

Will subjects participate in any study activity prior to parents/guardians physically signing a consent document?

No

q30334

Explain which parents/guardians will provide written signature as documentation of consent, and which will not.

Survey participants who enroll online will be asked for a printed (typed) signature.

q30333b

Explain the process for obtaining a written signature from parents/guardians.

Using the REDCap e consent platform parents/guardians will type their name in a signature box

q30335

Since some parents/guardians will not provide a written signature as documentation of consent, a waiver of documentation of parental/guardian consent is required. Choose the option which most appropriately applies to your study.

The research presents no more than minimal risk of harm to subjects AND involves no procedures for which written consent is normally required outside of the research

q942

Choose the option which most appropriately applies to your study.

Parental/guardian consent cannot be practicably obtained.

q943

Explain how the research involves no more than minimal risk to the subject.

FGID module, retrospective/prospective reviews: For the data reviews, parental consent cannot be practicably obtained as there are no study staff in clinic and attempting to reach each parents of so many patients is not feasible. There is a

minimal risk for loss of confidentiality but not beyond the risk of a routine clinic visit. No part of this research presents more than a minimal risk to subjects. Study team personnel have been trained in human subjects' research practices and HIPAA regulations (i.e. confidentiality, privacy and security practices). Furthermore, all data will be securely transferred and stored on fire-walled, encrypted and password-protected hard drives and databases, and locked file cabinets will be used to store any confidential paper study materials.

q944

Explain how the waiver will not adversely affect the rights and welfare of subjects.

FGID module, retrospective/prospective data reviews: There is a minimal risk for loss of confidentiality but not beyond the risk of a routine clinic visit. The subjects will continue to receive care as normal, waiver will not affect care provided. No part of this research presents more than a minimal risk to subjects. Study team personnel have been trained in human subjects' research practices and HIPAA regulations (i.e. confidentiality, privacy and security practices). Furthermore, all data will be securely transferred and stored on fire-walled, encrypted and password-protected hard drives and databases, and locked file cabinets will be used to store any confidential paper study materials.

q945

Explain how the research could not be practicably carried out if informed consent were required.

FGID module, retrospective/prospective reviews: The research could not be practicably carried out if informed consent of patients at clinic visits were required because there are no study staff on site to conduct the consent process. (Research staff are not based in the study clinics.) Additionally, informing patients that they are part of a study involving GI disorders may bias the results given to the clinician, and in turn, to the FGID module.

q30004i

Explain why the research could not be practicably carried out without identifiers.

FGID module: The research could not be practicably carried out without identifiers because GI screening questions are based on patient DOB/age. Survey(online and phone): The research could not be practicably carried out without identifiers because we are contacting patients who screened positive in clinic. A002 Tool usability

questionnaire: The research could not be practicably carried out without identifiers because we are only surveying family who have completed the module and meet our inclusion age and setting

q946

Explain how subjects will be informed of pertinent results at the conclusion of the study, if appropriate. If subjects will not be informed, enter N/A.

N/A

q950

In order to describe the process for obtaining assent from children, check all that apply.

Some/all children are not capable of providing assent.

Some/all children will not provide assent even though they are otherwise capable. A waiver of assent will be requested.

Some/all children will provide assent.

q951

Explain why children are not capable of providing assent. Consider age, maturity, and psychological state, and situations where capability is so limited that they cannot reasonably be consulted.

This research will include patients ages 0 through 17 and children age 0-6 are typically not considered mature enough to provide assent.

q952

Choose the option which most appropriately applies to your study.

Assent cannot be practicably obtained.

q953

Explain how the research involves no more than minimal risk to the subject.

FGID module: In clinic, patients and parents will be asked (but not required) to respond to yes/no questions about GI symptoms as part of standard care. There is a minimal risk for loss of confidentiality but not beyond the risk of a routine clinic visit.

Phone surveys: N/A - will get verbal assent from older patients

Retrospective reviews: There is only a minimal risk of loss of confidentiality as all data will be

securely accessed, transferred, and analyzed. A002 Tool usability questionnaire: There is a minimal risk for loss of confidentiality. The questions capture information about the user's interaction with the module.

q954

Explain how the waiver will not adversely affect the rights and welfare of subjects.

FGID module, retrospective/prospective reviews: There is a minimal risk for loss of confidentiality for the retrospective and prospective review of data but not beyond the risk of a routine clinic visit. Phone surveys: N/A (verbal consent/assent) A002 Tool usability questionnaire: Consent implied through agreement to participate

q955

Explain how the research could not be practicably carried out if child assent were required.

FGID module, retrospective/prospective reviews: The research could not be practicably carried out if informed assent of patients at clinic visits were required because there are no study staff on site to conduct the consent process. (Research staff are not based in the study clinics.) Additionally, informing patients that they are part of a study involving GI disorders may bias the results given to the clinician, and in turn, to CHICA. Phone survey: N/A (verbal consent/assent) A002 Tool usability questionnaire: The parent, parent/child dyad, or patient (add A003 "or patient") who filled out the tool will be presented with the SIS. The SIS will serve as a consent and assent tool, the questionnaire is targeted to the individual or individuals who completed the module.

q30004j

Explain why the research could not be practicably carried out without identifiers.

FGID module, retrospective/prospective reviews: The research could not be practicably carried out without identifiers because GI screening questions and are based on patient DOB/age. Retrospective reviews are based on patient DOB, symptoms, and diagnoses. Phone survey: The research could not be practicably carried out without identifiers because we are contacting patients who screened positive in clinic. A002 Tool usability questionnaire: The research could not be practicably carried out without identifiers because we are only surveying family who have completed the module and meet our inclusion age and setting

q956

Explain how subjects will be informed of pertinent results at the conclusion of the study, if appropriate. If subjects will not be informed, enter N/A.

N/A

q958

Describe the timing of the assent process, including how you will ensure children have sufficient opportunity to discuss and consider participation before agreeing to participate in the research.

Surveys Phone enrollment: After getting permission from the parent/LG to speak with the patient ages 10 through 17, the RA will verbally review the SIS/Auth with the youth at the same time it is reviewed with the parent, answer any questions, and call back later if s/he would like more time to consider participation. Online enrollment: In a brief introduction to the online consent process on the E-consent page, it is asked that the child age 10 and older review the online consent document with the parent. During the recruitment phone contact or online enrollment: If the parent has the desire to complete enrollment and the youth is unavailable, enrollment will proceed without assent to decrease burden on family and barrier to enrollment. A002 Tool usability questionnaire: After the parent, parent/patient dyad, or patient (add A003 "or patient") has completed the FGID module, they will receive communication offering the opportunity to provide voluntary feedback. If interested in providing feedback, they will be presented with the electronic SIS (in Notes and Attachments)

q959

Describe any assent tools which will be used to present information to potential subjects (i.e. assent document, study information sheet, videos, brochure, drug/device information, etc) and how they will be used.

Phone surveys: SIS/Auth form will be used for assent of patients 10 years and older. Will not seek assent for child < 10. Assent tool will be used for those 10-13 and consent form will be used for ages 14-17. Only verbal assent will be obtained. A002 Tool usability questionnaire: electronic SIS (in Notes and Attachments)

q996

Will children indicate their consent with a signature on an assent or consent statement?

Subjects will not provide a signature

K-HIPAA

q23253

Are you part of a covered entity (health care provider that transmits health information electronically) or are you receiving information from a covered entity as part of your research?

Yes

q23254

Will protected health information be utilized, accessed, collected, or generated as part of the study?

Yes

q30347a

Select the electronic systems to be used for the collection and/or storage of protected health information (ePHI). Choose all that apply.

REDCap

IU Box Health Data Account

q23257

Will you be accessing or collecting protected health information for RECRUITMENT purposes?

Yes

q23258

Choose all that apply to the recruitment plans.

Review of medical records by the study team

q23259

Will review of medical records for recruitment purposes be conducted by an investigator who is NOT a part of the potential subject's care team?

No

q23277

HIPAA applies to your study, and requires that you obtain authorization for PARTICIPATION in research, or that you request a waiver. Check all that apply.

I will obtain written, signed authorization from subjects prior to their participation  
 I will obtain authorization from subjects prior to their participation but subjects will not physically sign a document

I will not obtain authorization prior to their participation

q23650

List all data elements to be used or disclosed (do not refer to an attachment).

FGID Module: Data points collected for participation in the retrospective review of FGID module data include date(s) of visit, physician name, patient vitals and demographics, contact information, patient/parent answers to GI questions, who is answering the questions (parent or patient or both), and physician notes about GI diagnoses, treatments, and recommendations. Phone survey: In addition to the FGID data points above, we will use parent and patient answers to the phone survey along with parent-reported demographics. Baseline retrospective review: DOB, date/diagnosis (ICD codes), Eskenazi clinic(s) of care Health care utilization retrospective review: • The presence of outpatient sick visits within the CHICA system clinic for any complaint • The presence of outpatient sick visits within the CHICA system clinic with an associated GI billing code • The presence of visits to statewide providers, including inpatient hospital stays, outpatient clinic visits, and emergency room visits. • The occurrence of any GI-related testing and procedures – specifically radiologic, laboratory testing, endoscopy, and surgical procedures related to GI diagnoses • The use of any medications prescribed to treat Rome IV diagnoses – specifically acid-suppressants, antispasmodics, antidepressants, stool softeners and laxatives, and pro-motility agents. A005, regarding child subjects who age up to 18 while on the study, whose parents will continue to answer the phone survey on their behalf: Will proceed with the same data collection as prior to birthday. Will as before, collect responses from the FGID Module, phone survey responses and parent reported demographics for self (where applicable).

q23651

A waiver of the requirement for a written signature must be approved by the IRB. Explain how this research involves no more than minimal risk of loss of confidentiality to the subject.

No part of this research presents more than a minimal risk of loss of confidentiality to subjects. Study team personnel have been trained in human subjects' research practices and HIPAA regulations (i.e. confidentiality, privacy and security practices).

q23652

Describe the plan for protecting identifiers from improper use and disclosure.

All data will be securely transferred and stored on fire-walled, encrypted and password-protected hard drives and databases, and locked file cabinets will be used to store any confidential paper study materials.

q23653

Describe the plan to destroy identifiers at the earliest opportunity appropriate for the research, considering the purpose of the research and local data retention requirements.

We will destroy identifiers in the database (and any paper records) at the earliest opportunity appropriate for the research and allowable by law.

q23654

Confirm that the study team will assure identifiable PHI will not be re-used or disclosed to individuals outside the study team, except as required by law.

PHI will not be re-used or disclosed to individuals outside the study team, except as required by law.

q23655

Explain how the research could not be practicably conducted without waiver of authorization or alteration of authorization requirements.

The research could not be practicably carried out if authorization for the use of PHI were required because there are no study staff on site to conduct the informed authorization process. (Research staff are not based in the study clinics.) Regarding new waiver for child subjects who age up while on the study: Intent is to limit any

barriers to ongoing participation. In the event that the parent has been the main source of information for the phone surveys (for teen age 17), we wanted to minimize any disruptions.

q23656

Explain how the research could not be practicably conducted without access to and use of identifiable PHI.

The research could not be practicably conducted without access to PHI because we are identifying patients based on health information (FGIDs) and their connecting data across sources.

q23278

Will you be collecting information from subjects' medical records?

Yes, I have uploaded an Authorization template to the Attachments section.

q23693

Explain which subjects will sign a written authorization form and which subjects will not.

Surveys Phone enrollment: Parents will provide verbal authorization for use of their child's PHI via phone. (No one will provide written/signed authorization.) Online enrollment: Parents will provide electronic signature on the the REDCap E-consent to document consent and authorization to participate

q23694

Explain how the elements of authorization will be presented to potential subjects, including a description of any tools used.

The elements of authorization will be presented to parents via phone by review of the Authorization form. (Parents may also choose to receive a copy via mail with their gift card.)

Attachments

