### Funding Sources

Funding Source

NATIONAL INSTITUTE OF DIABETES, DIGESTIVE & KIDNEY

Conflicts of Interest

q134

Are any of the investigators listed in the personnel section aware of an institutional conflict of interest which could affect or be affected by this research?

No

q24901

Do any of the investigators listed in the Personnel section (or their immediate family members) have a significant financial interest which could affect this research?

No

q24905

Does the Principal Investigator affirm all investigators listed as personnel on this protocol have agreed to participate in this project, are aware of their status and role, and have been adequately trained to participate in the project?

Yes

A-Level of Review

q720

Does any research activity in this study present more than minimal risk to human subjects?

No. The research may qualify for Expedited review if all research procedures fall into one of the categories below.

q721

Check all category(ies) which apply to this research.

Category 5 - Research involving materials (data, documents, records, or specimens) that have been collected, or will be collected solely for nonresearch purposes  
Category 7 - Research on individual or group characteristics or behavior, or research employing survey, interview, oral history, focus group, program evaluation, human factors evaluation, or quality assurance methodologies

q724

Will the researchers be using a data collection form?

No

q725

List all data points that will be recorded or collected.

FGID Module: Data points collected for participation in the retrospective review of FGID module data include date(s) of visit, physician name, patient vitals and demographics, contact information, patient/parent answers to GI questions, who is answering the questions (parent or patient or both), and physician notes about GI diagnoses, treatments, and recommendations. Tool Usability Questionnaire: Data points collected in the Gastrointestinal Symptom Survey Tool and FGID Module (as above) Survey (online and phone): In addition to the FGID Module data points above, we will use parent and patient answers to the phone survey, along with parent-reported demographics. Baseline retrospective review: DOB, date/diagnosis (ICD

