codes), Eskenazi clinic(s) of care Health care utilization retrospective review: • The presence of outpatient sick visits within the Eskenazi system clinic for any complaint • The presence of outpatient sick visits within the Eskenazi system clinic with an associated GI billing code • The presence of visits to statewide providers, including inpatient hospital stays, outpatient clinic visits, and emergency room visits. • The occurrence of any GI-related testing and procedures – specifically radiologic, laboratory testing, endoscopy, and surgical procedures related to GI diagnoses • The use of any medications prescribed to treat Rome IV diagnoses – specifically acid-suppressants, antispasmodics, antidepressants, stool softeners and laxatives, and pro-motility agents.

q23340

Would identification of subjects and/or their responses reasonably place them at risk for any of the following (check any that apply):

None

B-Lay Summary Research Design

q22122

Describe the purpose of this study in lay terms, including research question(s) and hypothesis.

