**Primary Outcome Analysis:** The primary outcome is whether there was resolution of symptoms of a FGID by Rome IV criteria in children and adolescents or whether parental reassurance was achieved for infants. For this dichotomous outcome, we will use a non-linear mixed-effects model and will adjust for potential confounders (fixed effects) and clinic effects (random effects). To be specific, if  $Y_{ik}$  is a binary variable indicating whether the  $k^{\text{th}}$  patient in the  $i^{\text{th}}$  clinic was reported a resolution of FGID symptom, we have

$$\text{logit}(Y_{ik} = 1) = \alpha_i + \mathbf{X}_{ik}\beta, \text{ where } \alpha_i \sim N(0, \sigma^2).$$

The random component  $\alpha_i$  correlates outcomes of patients cared by the same clinic. Physicians would not be considered as a nesting factor since the same patients at different visits may not be seen by the same physician. The vector  $\mathbf{X}_{ik}$  represents fixed covariates and  $\beta$  represents the corresponding coefficients. The fixed covariates will include critical covariates such as treatment group, gender, and other patient and clinic level characteristics. We will also examine potential interaction terms among the covariates, particularly interactions between treatment arm and other covariates. If there is a significant treatment difference, we will report the 95% confidence interval of the treatment difference after adjusting for all confounding factors. The model will be fitted by the SAS procedure NL MIXED.

**Secondary Outcome Analyses:** The additional time points of 1, 6, and 12 months will be modeled identically to the primary outcome analysis. Furthermore, we will have a number of secondary outcomes which are count data aggregated within the 12 months after initial Rome IV

diagnosis. We will use Poisson regression to model these count data. To adjust for the possible differences between the intervention and control groups, we will use an approach similar to the analyses of primary outcomes and again clinic will be considered as a cluster factor to take into consideration the correlation in count data within each clinic. Family and provider satisfaction scores will be analyzed using Student's t-test, as well as a linear mixed-effects model as with other outcomes.

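### The listed health care utilisation data elements name neither event counts nor event dates, while the SAP models 12-month counts by Poisson regression

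*Protocol*

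**What the plan says.** Protocol, A-Level of Review, q725 carries the instruction "List all data points that will be recorded or collected". For the health care utilisation review the answer has five items:

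- Sick visits at the system's own clinics, given as "The presence of outpatient sick visits within the Eskenazi system clinic for any complaint".
- The subset of those visits that were billed under a GI code, again worded as presence.
- Care elsewhere in the state, given as "The presence of visits to statewide providers, including inpatient hospital stays, outpatient clinic visits, and emergency room visits".
- Investigations, given as "The occurrence of any GI-related testing and procedures"; the kinds of test and procedure are then named.
- Drug treatment, given as "The use of any medications prescribed to treat Rome IV diagnoses"; the drug classes are then named.

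Q724, just above, says that no data collection form will be used. Section K-HIPAA, q23650, which asks for all data elements and does not allow reference to an attachment, repeats the five items. There the clinic system carries a different name: "The presence of outpatient sick visits within the CHICA system clinic for any complaint". The IRB's description of PHI for the participation waiver (Administrative Details Form, item 9010) repeats them again.

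The SAP, Secondary Outcome Analyses, refers to "secondary outcomes which are count data aggregated within the 12 months after initial Rome IV" diagnosis. It models them by Poisson regression with clinic as the cluster factor. It does not say which counts these are.

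Protocol section B, q22122, makes lower use of medical services the secondary outcome. Aim 2 gives repeat outpatient visits and ED visits as examples.

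**The concern.** A 12-month count per child needs two things for each event: that it is recorded as a separate event, and that it has a date, so that it can be placed inside or outside the window. The utilisation items name neither. A programmer who built the extract strictly from q725 or q23650 could deliver one indicator per child and item, and the SAP's model would have no count to work on.

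At stake is the secondary hypothesis of reduced utilisation. An indicator of any visit cannot distinguish four visits from two, and a reduction in repeat visits is what Aim 2 describes. There is also a regulatory side. The waiver's own description of the PHI does not mention utilisation event dates, so an analyst who needs them would be using data that the approved list does not name.

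**Working it through.** No figure in the plan can be reproduced here: neither document gives a utilisation rate or a power statement for these outcomes. The check is a comparison of texts, followed by an illustration on assumed rates.

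**Comparison**

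| What the SAP's model needs | Where the protocol might supply it | Result |
|---|---|---|
| Number of events per child | q725, q23650 and item 9010, utilisation items | Presence, occurrence or any use; no number named |
| Date of each event | Same items | None named |
| Date of each event | q725, FGID Module | Visit dates are listed, in a form that allows more than one, but for the module data; they do not clearly cover statewide visits, tests or medications |
| Date of each event | q725, baseline review | Date and diagnosis, for the pre-implementation review only |
| Encounter-level source | Section B, q22123; section H, q30004b | Query of Epic and INPC; encounter data linked to past and prospective health data |
| Definition of each count | SAP, Secondary Outcome Analyses | Type and 12-month window given; counts not named |

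So q725 names dates for two other components and not for this one. The source can supply dated events, but the specification does not ask for them.

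**Illustration: what a flag would lose, if flags were all that was kept**

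Assumptions, none from the documents: visits per child follow a Poisson distribution with yearly mean λ of 0.5, 2 or 4, and the intervention multiplies the rate by 0.75.

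- Share of children flagged: P(any) = 1 − exp(−λ).
- Risk ratio seen on the flag: [1 − exp(−0.75λ)] / [1 − exp(−λ)].
- Fisher information on log λ: λ for the count, λ² exp(−λ) / [1 − exp(−λ)] for the flag. Share kept = λ / [exp(λ) − 1].

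At λ = 2: P(any) = 1 − 0.135 = 0.86. The risk ratio is (1 − 0.223) / (1 − 0.135) = 0.777 / 0.865 = 0.90. The share kept is 2 / (7.389 − 1) = 0.31.

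| Assumed λ | Flagged | Rate ratio 0.75 appears as | Information kept |
|---|---|---|---|
| 0.5 | 39% | 0.79 | 77% |
| 2 | 86% | 0.90 | 31% |
| 4 | 98% | 0.97 | 7% |

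The loss is modest for uncommon events and large for frequent ones.

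**The case against.** The strongest reply is that an IRB form lists domains of data and the SAP defines the variable. The items speak of visits in the plural. In several of them the word any qualifies the complaint or the drug and does not define a binary variable. Picking out visits with a GI billing code already requires codes to be matched to individual visits. The records are linkable at encounter level, and the SAP says plainly that the outcomes are counts.

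Much of this stands, and it rules out several stronger readings that a reader might infer:

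- *That utilisation is recorded as yes/no.* This is the literal sense of presence and occurrence, but no passage states such coding or says that dates will not be pulled.
- *That the counts cannot be derived.* They could be extracted from Epic and INPC.
- *That the module's dates cover the index visit only.* The wording is not limited to one visit.
- *That Poisson regression will be fitted to flags, with the wrong variance.* The SAP plans it for counts.
- *That nearly every child will have some visit, so a flag would sit at its ceiling.* The documents give no rates, and at an assumed mean of 0.5 only 39% would be flagged.

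It is also an inference that the SAP's unnamed counts are the q725 items. Aim 2 makes that a fair reading for visits, less clearly so for tests and medications.

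The reply does not supply the missing specification. Both questions ask for the full list, the wording appears three times, and no other passage names utilisation counts or event dates.

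**Conclusion.** The point holds as a mismatch of specification. Three lists give utilisation as presence, occurrence or any use without counts or event dates, while the SAP models 12-month counts that it does not define. Taken literally, the listed elements do not support the planned analysis; the underlying records could.

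The effect is confined to secondary outcomes. Its size is conditional on two things the documents do not settle: whether the extract would follow the list literally, and how often children attend. If only flags were kept, about 77%, 31% or 7% of the information would remain at assumed Poisson means of 0.5, 2 or 4 visits a year. These figures show a range and do not predict a loss in this trial. The point is worth settling before the data pull because the correction is cheap then.

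**What to change.** 1. In q725, q23650 and the matching PHI description (item 9010), list each utilisation event with its date, type and associated code. Use one name for the clinic system throughout, since q725 and the other two lists differ.
2. In the SAP, name each count outcome, its source (Epic or INPC), its date field, and the start and end of its 12-month window.
3. In the same query, take the 12 months before the index visit and enter each child's prior count as a covariate. Section H, q30004b already provides for linkage to past health data, and with only six clinics a cheap gain in precision is worth having. SAP Table 3 includes infant diagnoses, so some children will have less than 12 months of history. For them, use the time available, as a rate or as an offset.

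Step 3 is an improvement in precision and is not needed to resolve the mismatch; steps 1 and 2 do that.

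Cost: an IRB amendment to the wording, extra fields and a wider date range in a query that is already planned, and a short addition to the SAP. No patient contact is needed. The downside is that more identifiable dates are held, which the amended waiver description should state.
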